However, it is equally important to define what the term RRTIs means, as the parent's opinion and a doctor's point of view can differ significantly. When assessing RRTIs, in addition to their frequency, their course, duration, response to pharmacological treatment, cultivation of the pathogen as well as the development of complications are much more important. At the same time, the so-called "physiological morbidity of the child" must also be taken into account, which is considered to be:

- Children 3-5 years: 6 8 RTIs with mild course, good response to treatment, predominantly during the autumn and winter months
- **Children 6-12 years:** 2 4 RTIs with mild course, good response to treatment, predominantly during the autumn and winter months

The treatment of RRTIs consists not only from the treatment of each infection, but should be mainly aimed at their prevention. Therapeutic and preventive strategies should aim to support weakened immune system functions, e.g. by **immunomodulation**. Immunomodulation can be defined as therapeutic or preventive intervention in the activity of the immune system in order to achieve homeostasis.

In practice, various preparations of natural origin are used to prevent RRTIs, but only few of them have scientific evidence proving efficacy with a sufficient number of relevant clinical studies and observations that elucidate individual aspects of the mechanisms of action as well as proven efficacy and safety in the management of individual diseases. Vitamins, minerals, as well as many natural immunomodulatory preparations (phytotherapy, probiotics, prebiotics, biologically active polysaccharides) are most commonly used, while individual biological effects are important – anti-infectious, immunomodulatory, anti-inflammatory, antioxidant, etc. By using these preparations or their combination, a synergy of effects can be obtained in the treatment of the selected condition.

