- Active group: Imunoglukan P4H[®] chewable tablets (IMG[®] 50 mg + Zinc 5 mg + Vitamin D 10 μg in 1 tablet):
 - up to 25 kg of body weight 1 tablet once a day for 3 months
 - over 25 kg 2 tablets once a day for 3 months
 - Placebo group: Placebo chewable tablets (Zinc 5 mg + Vitamin D 10 μ g in 1 tablet)
 - o up to 25 kg of body weight 1 tablet once a day for 3 months
 - o over 25 kg 2 tablets once a day for 3 months

Discussion about design

Multicenter, prospective, randomized, double-blind, placebo-controlled study design is a perpective for obtaining clinically, scientifically and statistically significant results to elucidate the impact of the investigational product on primary and secondary endpoints. The 3-month duration of the study is justified in evaluating the modulation of the immune response and its clinical impact on such events as a reduction in the number of respiratory infections, shortening their duration, and reducing the need for ATB treatment. In addition to confirming the underlying hypothesis, the pilot study should also provide data on tolerability, safety and possible adverse effects.

Subjects enrolled in the study complete an anamnestic data collection and fill out relevant questionnaires during control visits.

Study endpoints

Primary endpoints – to evaluate the effect of pleuran administration (Imunoglukan P4H[®] chewable tablets) compared to the placebo group on reduction in the number of RTIs episodes (total number)

Secondary endpoints – to evaluate the effect of pleuran administration (Imunoglukan P4H[®] chewable tablets) compared to the placebo group on:

- reduction in the number of episodes of RTI subtypes
- reduction in the duration of RTI episodes (total duration, RTI subtypes)
- reduction of the need for antibiotic (ATB) therapy
- reduction of the number of missed days at school/nursery due to RTI
- reduction of the number of missed working days due to RTIs
- reduction of the number of emergency department visits due to RTI
- reduction of the number of physician visits due to RTI
- tolerability and safety

Inclusion criteria

- signed informed consent
- age 3-18 years
- history of recurrent respiratory infections:
 - Age 3 to 5 years (< 6 years): 6 or more upper or lower respiratory tract infections from October 2022 until the end of March 2023
 - Ages 6 to 18 years (≥ 6 years): more than 3 upper or lower respiratory tract infections from October 2022 until the end of March 2023

Exclusion criteria

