- refused informed consent
- bronchopulmonary dysplasia
- primary immunodeficiency
- cystic fibrosis
- chronic diarrhoea
- chronic diseases of the lungs, kidneys and liver
- malformations of the cardiovascular system
- oncological disease
- malnutrition
- intolerance to any of the ingredients in the study product
- taking preventive immunomodulatory therapy (beta-glucans, bacterial lysates, isoprinosine) less than 14 days prior enrolling the patient into the study

List of data collected from study subjects

Basic identification data	• Patient ID				
	 Patient Initials 				
	 Patient's Date of birth 				
	 Date of completion of CRF / Date of visit 				
Medical history and	o Age				
demographics	o Sex				
	 Current comorbidities 				
	 Current treatment of comorbidities 				
Diagnostic procedures	 Patient diary (Respiratory infections) 				
Primary endpoints	 RTIs incidence (total) 				
Secondary endpoints	 RTIs subtypes incidence 				
	 Duration of RTIs (total duration, RTIs subtypes) 				
	 The need for ATB therapy for the treatment of RTIs 				

	0	Number of missed days in school/nursery due to RTIs		
	0	Number of missed working days due to RTIs of the child		
	• Number of Emergency department visits due to			
	0	Number of Physician visits due to RTIs		
	0	Tolerability		
	0	Safety (occurrence of adverse events)		
Other data	0	Compliance		

Study visit and evaluation plan

Visit number	V0	V1	V2	V3
Day of visit	Initial	after 1 st month	after 2 nd month	after 3 rd month
	examination	(30 ±7 days)	(60 ±7 days)	(90 ±14 days)
Informed consent	Х			
Inclusion / exclusion	х			
criteria				
Demographics	Х			
Medical history	х			
Comorbidities	х	х	Х	х
Dispensing of study product	Х			
Incidence of respiratory tract infections (Patient diary)		Х	Х	х
Adverse events		Х	х	х
Returning the study product, product accountability and patient compliance				х

Required diagnostic procedures

Patient diary "Respiratory tract infections"

Parents or legal representatives of study subjects will record up-to-date data (incidence of infectious morbidity, symptoms, need for ATB therapy, physician or emergency department visits, number of missed days at school/nursery and work due to RTIs) throughout the study period. The filled "Patient diary" will be handed over to the treating physician at each visit.

Adverse event form

The physician fills out the Adverse event form when adverse events occur and records the occurrence of adverse events also in the CRF.

Compliance

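### Does the lack of a written rule for counting RTI episodes require a change to the protocol?

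*Combined protocol and SAP*

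**What the plan says.** Under Study endpoints, the primary endpoint is "reduction in the number of RTIs episodes (total number"). Secondary endpoints include "reduction in the number of episodes of RTI subtypes" and the duration of episodes, overall and by subtype. The List of data collected from study subjects repeats these as fields, for example "RTIs subtypes incidence", without a rule for deriving them.

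The source is described under Required diagnostic procedures: "Parents or legal representatives of study subjects will record up-to-date data (incidence of infectious morbidity, symptoms, need for ATB therapy", together with visits and missed days, throughout the study period. The same paragraph has the completed diary passed to the treating physician at each visit. Discussion about design adds that subjects "fill out relevant questionnaires during control visits".

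Three other places come close to a definition but are not tied to the endpoint. The Introduction lists clinical signs of respiratory infection as background. The Inclusion criteria speak of upper or lower infections when describing the child's history. The section on recurrent infections says that the term for recurrent disease needs defining, "as the parent's opinion and a doctor's point of view can differ significantly".

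**The concern.** A count endpoint is only as well defined as its unit. Two analysts given the same diary could count a relapse after a few good days as one episode or two. Parents at 36 centers could also differ on whether a runny nose qualifies. The protocol itself warns that parents and doctors see these illnesses differently, although it says so of the recurrent condition and not of single episodes.

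The children have frequent infections by selection: "6 or more upper or lower respiratory tract infections from October 2022 until the end of March 2023" below age 6, and "more than 3 upper or lower respiratory tract infections from October 2022 until the end of March 2023" from age 6. Closely spaced infections therefore seem likely, and a rule that merges them would remove more episodes from the arm with more infections, pulling the rate ratio towards 1. If the rule were chosen after unblinding, the 5% error rate would no longer hold. The subtype endpoints seem to lack even a list of categories.

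**Working it through.** **What can be reproduced.** The protocol gives no event rate, effect size, alpha or power, so the planned 250 children cannot be re-derived. Everything below rests on assumed inputs except the entry minimums, the 1:1 allocation (125 per arm) and the 90-day follow-up.

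**Entry rates.** October 2022 to the end of March 2023 is 182 days. Six infections give 6/182 × 90 = 2.97 per 90 days. More than 3 means at least 4, so 4/182 × 90 = 1.98.

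**Effect of a merging rule, with each illness treated as an instant.** Let L be the daily rate and g the onset-to-onset gap below which infections merge. The expected count in 90 days is L(90 − g)exp(−Lg) + 1 − exp(−Lg). With a true ratio of 0.75:

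| Placebo rate per 90 days | Gap | Placebo count | Fall | Ratio seen |
|---|---|---|---|---|
| 2.97 | 7 days | 2.38 | 20% | 0.793 |
| 2.97 | 14 days | 1.95 | 34% | 0.832 |
| 1.98 | 7 days | 1.71 | 14% | 0.778 |
| 1.98 | 14 days | 1.49 | 25% | 0.804 |
| 1.00 | 7 days | 0.93 | 7% | 0.764 |
| 1.00 | 14 days | 0.87 | 13% | 0.777 |

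Simulated power (dispersion 0.3) with no merging, 7 days and 14 days is 68%, 61% and 53% at 2 per 90 days, and 78%, 69% and 54% at 3. These losses come from imposing a merging rule. Leaving one out does not cause them: the count without merging has the highest power.

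**How far the model can be trusted.** It depends on illness having no length. At the entry rates it puts the next onset within 7 days in 1 − exp(−6 × 7/182) = 21% or 1 − exp(−4 × 7/182) = 14% of cases. But the history criteria count infections already judged separate. If each lasts 7 days without overlap, onsets within 7 days are 0%. Onsets within 14 days are then 1 − exp(−7/(182/6 − 7)) = 26% or 1 − exp(−7/(182/4 − 7)) = 17%, against 37% or 26% in the instant model. The documents give no illness length, so how often infections cluster cannot be settled.

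**The defect itself.** Suppose a share f of recorded placebo episodes is false and the same number per child is added on active. The ratio seen is 0.75 + 0.25f, or 0.775, 0.80 and 0.825 for f = 10%, 20% and 30%. Power follows from the log ratio divided by its standard error, where the squared standard error is the sum over arms of variance/(125 × mean²). Take 2 true episodes on placebo, dispersion 0.3, and false episodes independent of the child's true rate. Power is then 67.7% with none, and 64.3%, 60.3% and 55.8% at the three shares.

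**What a rule would recover.** If it removes every false episode but drops the same share of true ones, power becomes 64.6%, 61.1% and 57.0%. The gains are 0.3, 0.8 and 1.2 points. For f = 10%, the remaining means are 1.8 and 1.35, the squared standard error is (1/1.8 + 1/1.35 + 0.6)/125 = 0.0152, and 0.288/0.123 − 1.96 = 0.38, which gives about 64.6%.

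**Type I error.** With no true effect, each single count rejects in about 5% of trials. Accepting any significant result among the no-gap, 7-day and 14-day counts gives roughly 7% to 10%. Adding a count of physician-attended episodes (assumed share 0.3 to 0.7) gives 10% to 14%.

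**The case for a change.** The best argument for a change is that a primary count without a written unit is not one endpoint, and that fixing it costs about a page. The protocol provides an Appendix for amendments, the public text has no analysis section that names the count, and blinding during the trial does not stop someone choosing a counting rule afterwards. On that view the lack of a power gain is beside the point, because the benefit is a count fixed in advance.

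Part of this stands. The protocol text contains no episode rule and no closed subtype list, and settling the count before unblinding is ordinary good practice. But the inflated error rate needs someone to try several rules on unblinded data, and no passage points to that.

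The documents also supply no basis for a particular rule. One built on the Introduction's signs would include bronchial hyperreactivity, which a parent cannot observe, and leave out sore throat and ear pain. Requiring two signs would let congestion with a runny nose from allergy count, and allergy is not among the exclusions. A requirement of 3 symptom-free days after the last symptom would, for an assumed illness of 5 to 7 days, act like an onset gap of 8 to 10 days and cost about 6 to 17 points of power in the instant-illness model. If illnesses cannot overlap, the cost may be small.

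**Conclusion.** No change to the plan follows. The missing episode rule is a gap of detail that the analysts can fill sensibly. The plain reading is the number of episodes recorded in the diary, without merging, and upper versus lower is a natural subtype split already used in the Inclusion criteria. The forms not shown may already contain episode dates and subtype fields, parents record symptoms continuously, and a physician receives each diary about monthly.

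With the blind intact, inconsistent counting is expected to be similar in both arms. It adds noise or dilutes the effect and does not favour either arm. On the assumed inputs (2 true placebo episodes per 90 days, ratio 0.75, dispersion 0.3, 125 per arm), false episodes at 10% to 30% would cost 3 to 12 points of power, but a counting rule with equal losses of true episodes would win back only about 1 point. No document figure says whether the true share of false episodes is near this range.

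The conclusion assumes that the blind holds and that one count is settled before unblinding. The absence of a statistical analysis section is a separate matter and is not judged here.

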Study subjects will return the container with remaining study medication at V3 (visit after 3 months) to their treating physician, who will count the number of remaining tablets. The physician will record the result in CRF. Patients with <75% compliance will be excluded from the study due to lack of collaboration.

Appendices to the study protocol, other changes in the conduct of study

Any amendments to the Protocol will be made in the form of an Appendix to the Protocol. Changes to the study are not permitted. Any unexpected and sudden changes in the conduct of study will be recorded in the clinical report.

Privacy Policy

All patients in this study will be identified with a unique ID. Identification of the patient through this ID will not be possible. Only the monitor can validate the source data. The unique ID of a particular patient will only be known to the investigator or monitor. The personal identification data entered into this study will be: date of birth, gender and initials. The nature of personal data identifiers is governed by all relevant legislative requirements.

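### Children below 75% compliance on a tablet count made only at the final visit are excluded, and no analysis of all randomised children is stated

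*Combined protocol and SAP*

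**What the plan says.** The Compliance section sets the rule: "Patients with <75% compliance will be excluded from the study due to lack of collaboration". The measurement behind it is a single count of leftover tablets: "Study subjects will return the container with remaining study medication at V3 (visit after 3 months) to their treating physician". The Study visit and evaluation plan agrees. Its row "Returning the study product, product accountability and patient compliance" is marked at V3 and at no other visit. The Timeline places V3 at 90 ± 14 days and labels it completion.

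Outcome data are gathered whether or not tablets are taken. Parents keep the diary of infections, antibiotic use, visits and "number of missed days at school/nursery and work due to RTIs) throughout the study period", and the diary "will be handed over to the treating physician at each visit". For adverse events: "The physician fills out the Adverse event form when adverse events occur and records the occurrence of adverse events also in the CRF". Tolerability and safety are listed among the secondary endpoints, and the Discussion about design says "the pilot study should also provide data on tolerability, safety and possible adverse effects".

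The documents define no analysis set (all-randomised, full analysis or per-protocol), no primary analysis method and no handling of missing data. Nowhere do they say that an excluded child stays in any analysis.

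**The concern.** Compliance is observed after randomisation and may depend on what happens to the child, for example if tablets are stopped during an infection or because they are poorly tolerated. Removing children on that basis leaves two groups that were not formed by randomisation. With no true effect, the compliers-only comparison is biased only when exclusion is related to RTIs **and** that relation, or the share excluded, differs between arms. Blinding, and the same zinc and vitamin D content in both tablets, make a large difference unlikely. They do not rule one out, because the tablets still differ in pleuran. Without an all-randomised result a reader cannot tell which situation applies.

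Two further gaps follow from the same sentence. A child who has no tablet count at V3 cannot be classified. Read literally, exclusion from the study also takes low compliers out of the tolerability and safety endpoint, and they may include children who stopped because of intolerance.

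**Working it through.** **What the plan supplies.** 250 children, 1:1, so 125 per arm if balanced. No alpha, power, effect size, RTI rate, dropout or expected non-compliance is given. The 250 therefore cannot be reproduced, and every other input below is an assumption.

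**Step 1, direction and size by hand.** Let q be the share excluded in an arm, r the ratio of the RTI rate in non-compliers to that in compliers, and m the overall mean, equal in both arms (no true effect). The complier mean is m / (1 − q + q·r), and the apparent rate ratio (RR) is active over placebo.

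- 20% active and 10% placebo excluded, r = 1.5 in both: (0.90 + 0.15) / (0.80 + 0.30) = 1.05/1.10 = 0.955.
- 10% excluded in each arm, r = 2 in active and 1 in placebo: 1.00/1.10 = 0.909.
- 10% excluded in each arm, r = 1.5 in both: 1.05/1.05 = 1.00.
- 20% and 10% excluded, r = 1 in both: 1.00.

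With Poisson counts of mean 1.5 and 20,000 simulated trials, the compliers-only type I errors are 7.0%, 14.0%, 5.1% and 5.1%. With all randomised children they are 4.8% to 5.2%.

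**Step 2, exclusion driven by the child's own RTI count.** Counts are gamma-Poisson with variance = mean + 0.4 × mean², means 1.5 and 2.5, 125 per arm, 20,000 runs per cell (Monte Carlo standard error about 0.15 points at 5%). Exclusion follows a logistic model with the odds ratio (OR) per RTI shown, and its intercept is set to give the stated share. The test is two-sided at 5% on the log rate ratio. There is no true effect.

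| Exclusion mechanism | RR | Type I error |
|---|---|---|
| Same link and share in both arms | 1.00 | 5.1–5.4% |
| Unrelated to RTIs, 20% v 10% | 1.00 | 5.4% |
| OR 1.3 v 1.2, 10% excluded | 0.98 | 5.4–5.9% |
| OR 1.3 v 1.2, 20% excluded | 0.96–0.97 | 5.9–6.2% |
| OR 1.3 both, 20% active v 10% placebo | 0.95–0.96 | 6.0–7.5% |
| OR 1.3 both, 10% active v 20% placebo | 1.05–1.06 | 6.6–8.0% |
| OR 1.3 in one arm only, 10% excluded | 0.93–0.95 or 1.05–1.07 | 6.7–9.1% |
| OR 1.6 v 1.3, 20% excluded | about 0.92 | 9–11% |
| Extreme: OR 1.6 in one arm only, 20% excluded | 0.81–0.84 or 1.20–1.24 | 23–40% |
| All randomised children analysed | 1.00 | 5.0–5.4% |

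**Step 3, power.** Take a true RR of 0.75 in compliers and 20% excluded for reasons unrelated to RTIs. Compliers-only power is 47–59%. For all randomised children it depends on the benefit in non-compliers:

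- full benefit (RR 0.75): 56–69%;
- half (0.8 × 0.75 + 0.2 × 0.875 = 0.775): 47–59%;
- none (0.8 × 0.75 + 0.2 × 1 = 0.80): 37–48%.

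Power can move either way, so the argument for change is validity.

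**Step 4, unequal diary time.** Retaining children who stop early brings in partial diaries. With 20% partial in one arm and 10% in the other, and stopping times uniform, mean observed time is 0.90 against 0.95 of the full period. Raw counts then give 0.90/0.95 = 0.95 (or 1.05 reversed) with type I error 6.9–7.6%. With log observed time as an offset, RR is 1.00 and type I error 5.1–5.6%. Even among children who attend V3, follow-up can run from 76 to 104 days (104/76 = 1.37).

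**Step 5, denominator (minor).** The threshold has no stated denominator. Take one tablet a day and three months as 90 days. A child who took 70 tablets and is seen on day 104 scores 70/90 = 78% (kept) or 70/104 = 67% (excluded). A child who took 60 and is seen on day 76 scores 60/76 = 79% (kept) or 60/90 = 67% (excluded).

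**The case against.** The strongest reply is that the sentence sits under Compliance and says nothing about the primary comparison, and that the harm depends on assumed inputs. In a blinded trial with nearly matched tablets the arms may well behave alike, and then there is no bias. Moderate cells stay within about 0.92 to 1.07, and the mildest type I errors barely exceed simulation noise. All of that stands, and size alone would not settle the matter. It does not answer the main point: an exclusion made at the completion visit has no practical effect except on the data analysed, and nothing in the documents restores the children removed.

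Three narrower objections also have weight.

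- The all-randomised benchmark assumes usable diaries from the children judged uncooperative, and the protocol cannot guarantee these are complete. The offset was tested only for partial diaries unrelated to RTIs, so it has not been compared with the compliers-only analysis under equally informative missingness.
- A child with no diary time contributes nothing to a model with an offset, so the primary set is in practice all randomised children with some diary data.
- The safety point is a literal reading only. Adverse events are recorded at V1 to V3, and nothing says that recorded events are deleted.

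**Conclusion.** The rule is wrong as written and must be fixed before the arms are compared. That exclusion follows randomisation, rests on one count at V3, and is not offset by any stated all-randomised analysis comes directly from the text. That the primary comparison would be compliers-only is an inference, but the natural one.

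The size and direction of any bias cannot be derived from the documents. Under the assumptions shown it is nil when the arms behave alike and modest under moderate differences. It is large only in an extreme case that blinding makes unlikely. The priority rests on the validity of the primary comparison, not on that extreme case.

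**What to change.** Replace the exclusion sentence, by the Appendix route the protocol prescribes for amendments, with wording such as:

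> The primary analysis includes all randomised children in their assigned arm, regardless of tablet count. Diary and adverse-event data up to V3 are retained for children who stop tablets. Each child contributes the observed RTI count, with the log of observed diary time as offset. Children with no diary data are reported by arm with reasons. Adverse events of all randomised children are kept in the safety assessment, except for children known to have taken no tablet. Compliance below 75% defines only a supportive per-protocol analysis. Exclusions from it, including children without a V3 tablet count, are reported by arm with reasons.

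Minor: reconcile the three-month course with V3 at day 90 ± 14, then define the compliance denominator. Also state how observed diary time ends for a child who stops between visits. The data list contains "Date of completion of CRF / Date of visit" but no diary stop date, so the last visit at which a diary was handed in is a workable default.

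**Cost.** The change is essentially one of wording, since diary, adverse-event and visit-date collection is already planned. The offset commits the plan to a count model, which the documents do not yet name, and assumes that the RTI rate in unobserved time resembles that in observed time. The all-randomised estimate may lie closer to 1, with less power than compliers-only (37–48% against 47–59% if the 20% of non-compliers gain nothing).
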